5.3 Analysis methods

Statistical analysis will be mainly descriptive and focus on establishing the recruitment and retention rates that would indicate a trial is feasible, and to estimate parameters which will inform the sample size for the main trial. Recruitment, retention, and satisfaction rates will be presented by group with 95% exact confidence intervals.

Observed data from all randomised participants will be included in the analysis following the intention-to-treat principle.

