2.3 Sample size

The target sample size is 120 families, randomly allocated in a 1:1 ratio between trial arms. This will be sufficient to demonstrate the feasibility outcomes of recruitment, retention, and adherence with satisfactory precision, but also to generate proof-of-principle that the intervention is likely to prove effective to support a funding application for a definitive trial. Data from the pre-feasibility study supports an average reduction pre- post-intervention on the PSI parenting stress scale of 11.44 (SD 14.62), representing an effect size of ~ 0.8 on Cohen's scale. If a moderate to large effect size was replicated in comparison to a control group measured at similar time points, this would justify moving to a definitive trial. To determine a significant effect size of >0.5 on Cohen's scale (~ 7.3 points on the PSI parent scale) comparing intervention with standard of care, with 80% power and at a one-sided significance level of 0.05, would require 102 families to be evaluated. To allow for an

attrition rate of 10% (withdrawal/loss to follow-up) we will seek to recruit >114 families. In our small-scale test-run of 9 families, retention was 100% and attendance was 97%, with 8 families attending all sessions and one family missing 2 sessions due to work commitments.

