5.1.2 Pre-specified criteria for progression to a definitive RCT

The assessment for the next phase would consider progression criteria using a traffic light system if the Trial Steering Committee are satisfied that the following feasibility criteria are met (or can be reasonably mitigated with changes to the suggested protocol):

- *Recruitment: 0-25% = red; 26-50% = amber; 51-100% = green*
 - *Percentage of eligible parents invited who agree to participate.*
- *Retention: 0-50% = red; 50-70% = amber; 71-100% = green*

- *Percentage of those participating who complete the study.*
- *Satisfaction: 0-50%=red; 51-70%=amber; 71-100% =green*
 - *Percentage of those who express satisfaction with the session, as captured by the SPECIFiC session evaluation form.*
- *Estimated differences in primary outcome (PSI-4-SF total score) at 16 weeks: does not favour SPECIFiC=red; does not favour either SPECIFiC or TAU=amber; favours SPECIFiC = green.*

If red/amber results are obtained, the qualitative evaluation will be used to potentially remedy problems. Where it is deemed that identified problems cannot be managed, an RCT will not go ahead.

5.1.3 Secondary outcomes included in the SAP:

- MCID PSI-4-SF:
 - Estimate the difference in PSI-4-SF scores at 16 weeks with sufficient precision to inform a wider discussion around the clinical efficacy of the intervention and how the PSI-4-SF performs as a primary efficacy outcome for a future RCT.
- Data completeness:
 - Levels of missing data for the proof-of-concept primary efficacy outcome by timepoint
- Parent stress:
 - *(PSI-4-SF)* at Time 2 (8 weeks): to compare with the primary outcome (Time 3 PSI-4-SF) to determine whether intervention effects change over time. Note this outcome is only measured in the intervention group, due to the trial design (waitlist controls).
- Children's behavioural difficulties:
 - The Strengths and Difficulties Questionnaire (SDQ)
 - The Eyberg Child Behaviour Inventory (ECBI)

- Parents' psychological wellbeing:
 - *The Clinical Outcomes in Routine Evaluation–Outcome Measure (CORE-OM)*
- Parental mental health scale:
 - Depression Anxiety Stress Scales (DASS-21).
- Parenting self-efficacy:
 - Tool to measure Parenting Self-Efficacy (TOPSE)
- Group sizes

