5.2 Outcome definitions

All validated questionnaires will be scored according to the appropriate scoring manual, unless stated otherwise.

- **Parent stress** post-intervention extended follow-up (16 weeks) using the *Parenting Stress Index 4th edition Short Form (PSI-4-SF)*. This is a 36-item respondent-based rating scale, selected as a valid and reliable measure of internal stress and dynamics within a family system. It is highly cited, reliable instrument which has been used in similar studies. This is chosen as the candidate primary outcome at Time 3 (16-week extended follow-up) because the theoretical basis of the intervention assumes that there will be reduction in parent stress in the medium term.
- **Children's behavioural difficulties:** The Strengths and Difficulties Questionnaire (SDQ) and the Eyberg Child Behaviour Inventory (ECBI); are parent-reported measures, both well-established for measuring behavioural difficulties in children.

- **Parents' psychological wellbeing:** *The Clinical Outcomes in Routine Evaluation– Outcome Measure (CORE-OM)*, which measures change following psychological interventions. It covers subjective wellbeing, anxiety and depression, physical symptoms, effects of trauma, social isolation, life satisfaction, and risks to oneself and others.
- **Progression criteria – satisfaction:** Parents were asked to complete the SPECIFIC session evaluation form after each session of SPECIFIC, with 16 questions. Question 1 refers to the facilitators and is not included in the scoring. Questions 2 to 16 have five possible responses; Strongly disagree, Disagree, Neutral, Agree, Strongly agree, mapping to scores of 0 to 4 respectively. These will be summed, giving a total satisfaction score ranging from 0 to 60, with 60 indicating total satisfaction with that session. For each participant, their total scores from each of the seven sessions (or every session attended) will be averaged, giving each participant a single score ranging from 0 to 60. These scores will then be averaged across all participants and expressed as a percentage to which the progression criteria cut-offs can be applied.
- **EQ-5D-5L** was chosen as the preferred measure of health-related quality of life for intervention studies and its use will inform the health economics assessment in the feasibility trial and full randomized controlled trial.

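### SAP 5.3 gives satisfaction an exact (binomial) confidence interval, but 5.2 calculates satisfaction as a mean score with no count to which such an interval could apply

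*SAP*

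**What the plan says.** Three sections of the SAP bear on satisfaction.

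- **5.1.2 (progression criteria)** sets the bands, "Satisfaction: 0-50%=red; 51-70%=amber; 71-100% =green", and describes the quantity as "Percentage of those who express satisfaction with the session, as captured by the SPECIFiC session evaluation form". That is a proportion of people.
- **5.2 (outcome definitions)** gives the calculation. Fifteen items (questions 2 to 16), each scored 0 to 4, are added up for every session: "These will be summed, giving a total satisfaction score ranging from 0 to 60, with 60 indicating total satisfaction with that session". A participant's session totals are then "averaged, giving each participant a single score ranging from 0 to 60". Finally: "These scores will then be averaged across all participants and expressed as a percentage to which the progression criteria cut-offs can be applied". No threshold marks a participant as satisfied.
- **5.3 (analysis methods)** groups satisfaction with two true proportions: "Recruitment, retention, and satisfaction rates will be presented by group with 95% exact confidence intervals".

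**The concern.** An exact interval for a rate is found by inverting a binomial test on x successes among n independent units. Recruitment and retention have such an x. Satisfaction as calculated in 5.2 does not: it is a mean of bounded scores, and its sampling error depends on how much those scores vary between participants. The binomial interval never uses that spread.

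To carry out 5.3 as written, the analyst would have to invent a numerator. The obvious choice, the mean percentage times the number of participants, assigns the score the variance p(1-p). That is the largest variance a 0-100 score with that mean can have, reached only if every participant scores 0 or 60. Averages over 15 items and up to seven sessions will normally vary much less.

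At stake is how firm the satisfaction result appears to the Trial Steering Committee. The result itself is not affected.

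**Working it through.** **The plan's own figures.** The SAP gives no expected satisfaction level, no SD for the score and no interval width, so there is no satisfaction figure to reproduce. The number of families is needed. Section 2.3 states: "The target sample size is 120 families, randomly allocated in a 1:1 ratio between trial arms". That is 120/2 = 60 per arm, or 60 × 0.90 = 54 after the plan's 10% attrition. The plan's sample size itself reproduces: effect size 0.5, 80% power and one-sided 0.05 give 50.15 per arm by the t-test method, so 51 per arm and 102 in all; 102/0.90 = 113.3, rounded up to 114.

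**Assumptions.** Between-participant SD of 5 to 25 percentage points, mean of 75% to 90%, and one score per family, independent between families.

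**Formulas.**
- Exact (Clopper-Pearson): lower limit = Beta quantile 0.025 with parameters (x, n-x+1); upper limit = Beta quantile 0.975 with parameters (x+1, n-x); x = n × mean/100. At n = 54 and 75%, x = 40.5, which is not even a whole number; the formula is used as it stands.
- t interval for a mean: full width = 2 × t(0.975, n-1) × SD/√n.

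**Largest possible SD.** √(0.75 × 0.25) = 43.3 points at a mean of 75%, and √(0.90 × 0.10) = 30 points at 90%. The binomial interval in effect assumes these values.

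**n = 54, mean 75%.** The exact interval is 61.3% to 85.8%, a width of 24.4 points. With t(0.975, 53) = 2.006 and √54 = 7.348:

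| SD (points) | t width (points) | exact width / t width |
|---|---|---|
| 5 | 2.7 | 9.0 |
| 8 | 4.4 | 5.6 |
| 15 | 8.2 | 3.0 |
| 25 | 13.6 | 1.8 |

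**n = 60.** At 75% the exact interval is 62.1% to 85.3%, 23.1 points wide, and the ratios to the t width are 9.0 (SD 5), 4.5 (SD 10), 3.0 (SD 15) and 1.8 (SD 25). At 90% it is 79.5% to 96.2%, 16.7 points wide, and the ratios are 6.5, 3.2, 2.2 and 1.3 for the same SDs. Over the whole grid the factor runs from about 1.3 to 9.

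**Course groups.** Section 2.1 says delivery is in groups of six, so scores may be correlated within a group. With an assumed intraclass correlation (ICC) of 0.1 the variance grows by 1 + 5 × 0.1 = 1.5. Nine groups (54/6) leave 8 degrees of freedom, with t = 2.306. The t width then grows by √1.5 × 2.306/2.006 = 1.41. With an ICC of 0.2 the growth is √2 × 2.306/2.006 = 1.63. At 75% and n = 54, the exact interval is then about 4.0 times (SD 8) to 2.0 times (SD 16) as wide at ICC 0.1, and about 3.4 to 1.7 times at ICC 0.2. In an extreme corner the excess disappears: at 90%, SD 25 and ICC 0.1, the exact width is 17.7 points against 13.6 × 1.41 = 19.2. The direction of the error is therefore assured only for independent families.

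**Mean score and count are different quantities.** If every parent answered Agree to every item, 5.2 would give 15 × 3 = 45 out of 60, or 75%, while a count of satisfied parents could be 100%. The choice between 5.1.2 and 5.2 is thus more than a matter of wording.

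**The case against.** The strongest reply is that no decision uses this interval. Section 5.2 applies the cut-offs to the averaged percentage itself, and dummy Table 2c has columns only for the result and its colour. This stands. A reader might infer that the wide interval could turn a green result amber, or make it fail to clear 70%. The SAP contains no rule that compares a confidence limit with a cut-off, so that inference is not supported.

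A second reply is that 5.1.2 speaks of a percentage of people and 5.3 of rates, and an exact interval is right for those. This also stands in part: if the conflict is settled in favour of a count, the interval in 5.3 is correct. It does not rescue the present text, because 5.2 is the only place where the calculation is spelled out, and it says its figure is the one to be set against the cut-offs.

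Two further readings go too far. One is a fixed multiplier, such as three to six times too wide. That needs an SD of about 7.5 to 15 points and a mean near 75%, neither of which the SAP gives. The other is that the interval could be far too narrow. That would require treating the 60 score points of each family as independent binomial trials, which nothing in the SAP suggests.

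Finally, the SAP does not write the word binomial. It is the ordinary meaning of an exact interval for a rate, and the sentence covers two proportions as well.

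**Conclusion.** The point holds, and it is minor. The interval named in 5.3 does not fit the quantity calculated in 5.2, and 5.1.2 describes a third thing, a proportion of people, that would fit it. With participants as the binomial n, the exact interval is about 1.3 to 9 times as wide as a t interval. This rests on assumed values: 54 to 60 independent families, SD 5 to 25 points and mean 75% to 90%. Correlation within course groups makes the factor smaller. The consequence is a misstated precision for one of the four progression criteria, with the colour rating unchanged.

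**What to change.** In 5.3, limit the exact (Clopper-Pearson) interval to recruitment and retention. For satisfaction, choose one of two routes and make 5.1.2, 5.2 and 5.3 agree.

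1. **Keep the mean score of 5.2.** Report it with a t-based or bootstrap 95% confidence interval computed from the participant-level mean scores, preferably allowing for course group, and reword 5.1.2 to describe a mean percentage score.
2. **Use a proportion, as 5.1.2 is worded.** Define a satisfied participant by a threshold on the score, report the count out of all participants, and keep the exact interval. Section 5.2 then needs rewording.

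The cost is a sentence or two of SAP text and a line of code; no new data are needed. Allowing for course group gives a somewhat wider interval than a simple t interval, about 1.4 times at the assumed ICC of 0.1. The second route needs a threshold that the SAP does not yet contain.

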5.3.1 Primary outcome analysis

Primary analysis (ITT)

Candidate outcomes for the definitive trial including Parent stress (PSI-4-SF) will be compared between groups using a mixed model approach including all observed data at 16 weeks and adjusting for baseline measures and recruiting site. A binary variable will be included as fixed effect to indicate treatment allocation. Site, cohort, and baseline measure will be included as covariates; all control participants will be allocated a single cohort indicator. Inclusion of random subject effects will account for correlation between repeated outcomes on individual families. Estimated differences between groups and their 95% confidence intervals will be presented. The lower level of the 95% confidence interval for the difference between groups not ruling out an adjusted difference between groups of 7.3 points on the PSI-4-SF (as per the sample size calculation, section 3.4) will be considered sufficient to demonstrate proof-of-concept in the intervention. Subgroup analysis, such as whether outcomes differ according to time from diagnosis or age of index child will inform inclusion criteria and potential stratification factors for a larger trial. The PSI-4-SF outcome will also be available at 8 weeks in the intervention group only and will be reported; these data will not be included in the primary endpoint analysis. We will examine outcome profiles within the intervention group to see if any treatment effect is maximal during

training. These analyses are exploratory in nature and intended to help inform future research.

Per-protocol analysis

Sensitivity analyses will be conducted on the primary outcome to assess the robustness of results to failure to adhere to the protocol.

Per-protocol analysis for the candidate primary outcome (PSI-4-SF) will be performed to analyse the difference between arms in those parents and children where the family was deemed to be protocol compliant (see definition in Section 3.3). Per-protocol analyses will not be carried out for secondary outcomes.

Subgroup analyses

Subgroup analysis, such as whether outcomes differ according to time from diagnosis or by the age of the child will be done by adding the relevant factors to the mixed model as additional covariates and including an interaction term. The results from these analyses will inform inclusion criteria and potential stratification factors for a larger trial.

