2.1 Trial design

A two-arm randomised feasibility study of SPECIFiC training course against waitlist controls. The control group will receive treatment as usual during the intervention period and will receive the parenting intervention after the intervention period (see appendix A of the protocol). Families will be randomised 1:1 into the intervention or control arm. The study will not affect any aspect of the participants' clinical care. The 7-week course will be delivered by trained facilitators, following the manual created in a prior study funded by the Medical Research Council (MRC). All materials and information are incorporated into this

SPECIFiC_SAP_V2.0 20th November 2024

manual. The intervention was set up to be delivered online to groups of 6 on a rolling basis. This will minimise wait times and allow for timely access to the intervention for the controls, who will be on a waitlist. All participants are to be eventually offered the intervention. The primary outcome measure for efficacy (Parenting Stress Index, PSI) will be used to compare the SPECIFIC arm against treatment as usual at 16 weeks. Following this, those on the control group will receive the intervention. See Appendix A (protocol) for the trial flowchart.

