2.2 Randomisation

Following a protocol amendment on 22 November 2023 (V3), the randomisation protocol was simple 1:1 allocation of families (index child and parent(s)) to (a) intervention arm or (b) waiting list control arm, using the online randomisation service SealedEnvelope.com. Prior to the protocol amendment, randomisation was balanced across cohorts of twelve (six in the intervention group, six waiting list controls).

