5.3.2 Secondary outcomes analyses

Analysis of other questionnaire outcomes, such as the SDQ, DASS etc. will be summarised by group using the appropriate summary measures and compared between groups using a mixed model approach as described above. Estimated difference and 95% confidence interval will be presented for each outcome.

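### With all controls in one cohort level, fitting cohort as a categorical fixed covariate (the natural reading of section 5.3.1) makes the treatment effect inestimable

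*SAP*

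**What the plan says.** SAP section 5.3.1 defines the primary efficacy model for PSI-4-SF at 16 weeks. On treatment: "A binary variable will be included as fixed effect to indicate treatment allocation". On the other terms: "Site, cohort, and baseline measure will be included as covariates; all control participants will be allocated a single cohort indicator". The only random effect named is for subject: "Inclusion of random subject effects will account for correlation between repeated outcomes on individual families". The 8-week scores exist in the intervention arm only, and of them the section says "these data will not be included in the primary endpoint analysis". The promised output is: "Estimated differences between groups and their 95% confidence intervals will be presented". That interval is then judged against 7.3 points for proof-of-concept, and the same difference feeds the PSI-4-SF traffic light in section 5.1.2.

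On cohorts, section 2.1 says: "The intervention was set up to be delivered online to groups of 6 on a rolling basis". Section 2.2 says that before the V3 amendment "randomisation was balanced across cohorts of twelve (six in the intervention group, six waiting list controls". Section 5.3.2 has the other questionnaires "compared between groups using a mixed model approach as described above".

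The SAP does not say whether cohort is fixed or random, whether it is nested within the intervention arm, or whether its coefficients are constrained.

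**The concern.** Once all controls share one cohort level, knowing a family's cohort means knowing its arm. A categorical cohort covariate then carries all the information in the treatment indicator, and a model with both has no unique treatment coefficient. The analyst would get either no treatment effect or one that depends on which level the software happened to drop.

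At stake is the between-arm difference for a listed primary outcome, together with its interval, the 7.3-point rule and the PSI traffic light. The secondary outcomes inherit the problem. Families taught together in groups of six may also have correlated outcomes. A cohort term is the natural place to allow for that, but this specification does not do so properly.

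**Working it through.** **The plan's own figure.** For a 0.5 SD difference, one-sided 0.05 and 80% power, the t-test needs 50.15 per arm, so 51 per arm and 102 families. Allowing 10% attrition, 102/0.9 = 113.3, so 114. Both match section 2.3. The calculation makes no allowance for delivery groups, and the present point does not change it.

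**Inputs.**
- From the SAP: 1:1 allocation, target 120 families (60 per arm), groups of 6, SD 14.62 (variance 213.7; this is the SD of pre-post change in the pre-feasibility study).
- Assumed, because the SAP does not give them: every group has exactly six families, giving 9 intervention cohorts at 51 per arm or 10 at 60 per arm; three sites, in the rank check and simulation only; ICC for delivery group of 0.01 to 0.10.

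**Step 1, cohort as a categorical fixed covariate.** Let T be treatment and C1 to CK the intervention-cohort dummies, with controls as the reference level. Every intervention family is in exactly one cohort and no control is in any, so T = C1 + … + CK. Adding a constant to the treatment coefficient and subtracting it from every cohort coefficient leaves the fitted values unchanged. Only the sums (treatment + cohort k) are identified. Rank of the design matrix:
- Intercept, treatment, 10 cohort dummies, baseline: 13 columns, rank 12.
- The same with site, 60 per arm: 15 columns, rank 14.
- With site, 51 per arm, 9 cohorts: 14 columns, rank 13.
- Without cohort: 5 columns, rank 5.

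The deficiency is always one and needs none of the assumed numbers.

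**Step 2, what software then reports.** If treatment is dropped, there is no effect estimate. If cohort k is dropped, the treatment coefficient is cohort k against all controls:
- Single cohort: 14.62 × √(1/6 + 1/60) = 6.26.
- Arm contrast: 14.62 × √(1/60 + 1/60) = 2.67.

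In one simulated data set (51 per arm, baseline correlation about 0.5) the coefficient ran from −6.9 to −15.9 depending on the cohort dropped, against −12.1 without cohort. Over 300 simulated data sets the mean SE was about 5.5 with a cohort dropped and 2.5 without cohort.

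**Step 3, effect on the 7.3-point rule.** Take benefit as positive and read the rule as met unless the whole interval lies below 7.3. At SE 6.26 the half-width is 1.96 × 6.26 = 12.3, so any estimate above 7.3 − 12.3 = −5.0 passes. At SE 2.67 the half-width is 5.2, so the estimate must exceed 2.1. On this reading, lost precision makes the rule easier to meet.

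**Step 4, cohort as a random intercept in both arms, controls as one cluster.** With between-cohort variance ICC × 213.7, K = 10 and known variances:
- One control cluster: variance = ICC × 213.7 × (1 + 1/10) + (1 − ICC) × 213.7 × 2/60.
- Partially nested: variance = ICC × 213.7/10 + (1 − ICC) × 213.7/60 + 213.7/60.

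| ICC | SE, one control cluster | SE, partially nested |
|---|---|---|
| 0.01 | 3.1 | 2.7 |
| 0.05 | 4.3 | 2.8 |
| 0.10 | 5.5 | 3.0 |

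At ICC 0.05 the sums are 11.76 + 6.77 = 18.52 and 1.07 + 3.38 + 3.56 = 8.02. At ICC 0 both give 2.67. Treatment is estimable here, but the control cluster's variance does not shrink as controls are added.

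**The case against.** The section speaks of a mixed model and attaches the word fixed only to treatment. With one 16-week outcome per family, a subject effect cannot be separated from residual error, so one might suppose that cohort was the intended random term. A reader might therefore infer from this point that the treatment effect is inestimable under any reading. The SAP does not support that: it never says cohort is fixed, and a random cohort effect leaves treatment estimable. What stands is that cohort is listed as a covariate beside site and baseline, and that subject is the only random effect named.

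A reader might also infer that making cohort random cannot help, or that the shared control code is itself the error. Neither follows. If the random term is restricted to the intervention arm, the cohort effect is multiplied by zero in controls and their code is harmless. The SAP does not state that model.

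Nor may one say that cohorts exist only in the intervention arm. The earlier randomisation cohorts of twelve spanned both arms and would not be collinear with treatment. The single control indicator rules them out as the covariate meant here.

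Other escapes are possible but unstated. Cohort as a linear number gives full rank but has no clear meaning. An average of the cohort-versus-control contrasts could be recovered from the fit, but no weights are defined, so the choice would be made at analysis.

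Finally, this is a feasibility trial that does not seek to show superiority. PSI-4-SF is one of four progression criteria, judged by the Trial Steering Committee, and recruitment, retention and satisfaction are untouched. That limits the consequence but does not remove the need for an estimable model.

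**Conclusion.** The model needs correcting as written. On its natural reading, with cohort as a categorical fixed covariate, the arm difference promised in section 5.3.1 cannot be estimated, and nothing elsewhere in the SAP repairs this. That conclusion is algebraic and rests on no assumed figure. On the alternative reading, a random intercept across both arms with one control cluster, the effect is estimable but imprecise whenever the cohort variance is above zero.

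The sizes are illustrative: SE about 6.3 against 2.7 on the first reading, and 4.3 against 2.8 on the second at ICC 0.05. They assume 60 per arm without attrition, cohorts of exactly six, SD 14.62 and no gain from baseline adjustment. The second pair also rests on an ICC that the SAP does not give.

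It would go too far to conclude that the whole progression decision fails. The defect reaches the PSI-4-SF estimate, the rules built on it and the secondary questionnaire comparisons.

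**What to change.** Before the final analysis, remove cohort from the list of fixed covariates in section 5.3.1 and state a partially nested model: fixed treatment, baseline score and site, plus a random delivery-group effect in the intervention arm only. One way to write it is a random coefficient on the treatment indicator by group, with no random intercept for group; the control code then does not matter. State in section 5.3.2 that the secondary outcomes use the same model.

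The cost is SAP wording and a small change to the Stata code, with no new data. The SE may be slightly larger than in a model that ignores delivery groups (in the illustration, 2.7 to 3.0 against 2.67 for ICC 0.01 to 0.10). A small-sample degrees-of-freedom method and a factor for the earlier randomisation blocks are optional additions and are not needed to repair the defect.
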